5.1.6.3 Concomitant medications

The dates of concomitant medications are imputed in the same way as AEs.

5.1.6.4 Last survival date

If the investigator is not informed of subject's death by the cutoff date of analysis, the latest complete date of the following data will be used as the last survival date:

- The dates of the subject's all assessments
- The start and end dates of new anti-tumor treatment after the discontinuation of study treatment
- The start and end dates of AEs
- The date of the last known survival status of the subject on the survival follow-up page
- The start and end dates of study treatment
- The date of withdrawal of informed consent form
- The date on the study discontinuation page (if the reason for discontinuation is "lost to follow up", the date of lost to follow up will not be calculated)

Only the date of actual examinations can be used to derive the last survival date. The dates of examinations and evaluations carried out after the cutoff date will not be used to derive the last survival date.

5.1.6.5 Death date

- If the day of the death date is missing, the day will be imputed with the last day of the month or the last survival date + 1, whichever is later;
- If the month and day of the death date are missing, the day will be imputed with 1 Jan. of the year or the last survival date + 1, whichever is later;
- If the death date is completely missing, the day will be imputed with the last survival date + 1.

5.1.6.6 New anti-tumor treatment

If the start date of a new anti-tumor treatment is not completely missing, it will be imputed according to the following rules and used to derive the end date of the study treatment. The date of PD mentioned below is date of the first documented PD.

- If the end date of the new anti-tumor treatment is partially missing or not missing, the end date of the new anti-tumor treatment will be used to derive the start date of the new anti-tumor treatment
 - If the month and day of the end date of the new anti-tumor treatment are missing but the year is not missing, 31 Dec. is used as the end date of the new anti-tumor treatment.
 - If only the day of the end date of the new anti-tumor treatment is missing, the last day of the month will be used as the end date of the new anti-tumor treatment.
- If the month (MM) or day (DD) of the start date of new anti-tumor treatment are missing or the date of the start date of new anti-tumor treatment is completely missing, the rules for deriving and imputing the date are as follows:
 - If the start date of a new anti-tumor treatment is completely missing, the imputed start date = $\min [\max (\text{PD date} + 1, \text{date of the last dose} + 1), \text{end date of the new anti-tumor treatment}]$
 - Only the year (YYYY) of the start date of new anti-tumor treatment is not missing
 - 1) If $\text{YYYY} < \min (\text{year}) [\max (\text{PD date} + 1, \text{date of last dose} + 1), \text{end date of new anti-tumor treatment}]$, the date is imputed as 31 Dec., YYYY.
 - 2) If $\text{YYYY} = \min (\text{year}) [\max (\text{PD date} + 1, \text{date of the last dose} + 1), \text{end date of new anti-tumor treatment}]$, the imputed date = $\min [\max (\text{PD date} + 1, \text{date of the last dose} + 1), \text{end date of new anti-tumor treatment}]$.
 - 3) If $\text{YYYY} > \min (\text{year}) [\max (\text{PD date} + 1, \text{date of the last dose} + 1), \text{end date of new anti-tumor treatment}]$, then the imputed date = 1 Jan. YYYY.
- The year (YYYY) and month (MM) of the start date of new anti-tumor treatment are not missing
 - If $\text{YYYY} = \min (\text{year}) [\max (\text{PD date} + 1, \text{date of the last dose} + 1), \text{end date of new anti-tumor treatment}]$, and if $\text{MM} < \min (\text{month}) [\max (\text{PD date} + 1, \text{date of the last dose} + 1), \text{end date of new anti-tumor treatment}]$, the date will be imputed with the last day of MM.

- If YYYY = min (year) [max (PD date + 1, date of the last dose + 1), end date of new anti-tumor treatment], and MM = min (month) [max (PD date +1, date of the last dose +1), end date of new anti-tumor treatment], the date imputed = min [max (PD date + 1, date of the last dose + 1), end date of new anti-tumor treatment].
- If YYYY = min (year) [max (PD date + 1, date of the last dose + 1), end date of new anti-tumor treatment], and if at the same time MM > min (month) [max (PD date +1, date of the last dose +1), end date of new anti-tumor treatment], then the imputed date = 1 MM, YYYY.
- If YYYY < min (year) [max (PD date + 1, date of the last dose + 1), end date of new anti-tumor treatment], then the day of the imputed date is the last day of MM.
- If YYYY > min (year) [max (PD date + 1, date of the last dose + 1), end date of new anti-tumor treatment], then the imputed date = 1 MM, YYYY.

All imputed dates must be before the date of withdrawal of informed consent form, lost to follow-up, and death.

Missing data of laboratory evaluations are not imputed.

The rules for imputation of missing data for the remaining study endpoints will be detailed in the specific sections of analyses.

5.2 Study Subjects

5.2.1 Disposition of subjects

All enrolled subjects will be divided by stage and dose group using frequency and percentage. In addition, in the disposition of subjects, the frequency and percentage of the following information will be summarized by dose group:

- Number of screened subjects and reasons for screening failure;
- Number of enrolled subjects;
- Number of subjects with study termination/treatment discontinuation;
- Reasons for study termination/treatment discontinuation;

Reasons for screening failure, subject enrollment, treatment discontinuation and reasons, and study discontinuation and reasons will be listed.

A listing will be provided on whether the enrolled subjects are included in the FAS, PPS, SS, ADAS, and TMKS. The listing will include rejected analysis sets and reasons for rejection at least.

5.2.2 Demographics and baseline characteristics

5.2.2.1 Demographics

The subjects' age, gender, ethnicity, height, weight, and body mass index will be summarized using descriptive statistics. Quantitative variables such as age, height, weight, and body mass index will be summarized using descriptive statistics such as number of evaluable subjects, mean and standard deviation, median, minimum and maximum. Categorical variables such as gender and ethnicity will be summarized using descriptive statistics, including number of evaluable subjects per category and corresponding percentage in total population.

5.2.2.2 Other baseline characteristics

The subjects' allergy, smoking, and alcohol history will be summarized and listed using descriptive statistics.

The diagnosis of small cell lung cancer in the subjects, including the VALG stage of the initial diagnosis, presence of metastases, course of disease, and time to the most recent progress/recurrence will be summarized using descriptive statistics. The course of disease (month) is defined as the time from the date of first pathological diagnosis to the date before the first dose, calculated as: (date of the first dose – date of the first pathological diagnosis) / 30.4375. The time to the most recent progress/recurrence (month) is defined as the time from the most recent progress/recurrence to the date before the first dose, calculated as: (date of the first dose – date of the most recent progress/recurrence) / 30.4375. The date of the first diagnosis, location of the primary tumor, location of the metastasis, diagnostic method, the VALG stage of the first diagnosis, date of the most recent progress/recurrence, course of the disease, and time to the most recent recurrence/progress will be listed.

5.2.3 Prior illnesses

Medical history will be coded by system organ class (SOC) and preferred term (PT) in the Chinese version of the ICH Medical Dictionary for Regulatory Activities (MedDRA) 21.0.

The prior illness of the subjects will be statistically summarized correspondingly by treatment group.

All prior illness will be listed.

5.2.4 Prior treatment and concomitant medication

5.2.4.1 History of anti-tumor treatment

History of anti-tumor treatment mainly includes systemic anti-tumor treatment, radiotherapy, and surgery, which correspond to history of anti-tumor treatment, radiotherapy history, and surgical history, respectively.

Anti-tumor treatments are descriptively summarized by the following categories, and the numbers and percentages of subjects undergoing corresponding anti-tumor treatment are calculated:

- Classification and indication of systemic treatment
- Number of systemic regimens (using different chemotherapy drugs) received in the past
- Indication of radiotherapy
- Type of surgery and classification of tumor surgery

The duration between the end date of the last anti-tumor treatment and the time (months) of the first dose will be summarized, calculated as: (date of the first dose – end date of the last anti-tumor treatment) / 30.4375.

All treatment histories (including anti-tumor treatment and non-anti-tumor treatment) are listed in detail.

5.2.4.2 Prior/concomitant medication

A list of prior medications and concomitant medications will be provided.

5.2.5 New anti-tumor treatment

The number and percentage of subjects who have received new anti-tumor treatment after withdrawal will be summarized by dose group, and a detailed listing will be provided.

5.2.6 Protocol deviations

Before database locking, data of all subjects on the eCRF will be checked for important protocol deviations. All potential important protocol deviations will be reviewed and evaluated by the investigator and the sponsor.

All important protocol deviations will be summarized and described by type and tabulated for analysis.

Definitions of important protocol deviations:

- Serious violation of the inclusion/exclusion criteria;
- Incorrect treatment by study drugs (not treated using the drug or dose as per randomization);
- Other protocol deviations jointly recognized by the investigator and the sponsor.

5.3 Extent of Exposure and Treatment Compliance

Based on the SS, the use of study drugs will be summarized using descriptive statistics by drug and dose group. The use of all study drugs will be listed in detail.

5.3.1 SHR-1210

Compliance (%) = (actual number of doses / scheduled number of doses) \times 100%

Scheduled number of doses = scheduled duration of administration / 14 (days).

The frequency and reasons of SHR-1210 treatment interruption and permanent discontinuation will be summarized.

5.3.2 Apatinib

Actual dose (tablets): The sum of the documented actual doses of a subject during the treatment period, calculated as the actual number of days of administration \times 1 tablet/day. The actual number of days of administration is subject to the records of apatinib administration. The number of consecutive dosing days for each period is calculated as: end date – start date + 1.

Scheduled dose (tablets): number of treatment cycles during the treatment period \times scheduled number of days of administration \times 1 tablet/day. One treatment cycle contains 28 days.

Apatinib Treatment Cycle	Scheduled Number of Days of Administration in Each Treatment Cycle
QD	28
QD (5 days on, 2 days off)	20
QD (7 days on, 7 days off)	14

Subject compliance (%) = (actual dose / scheduled dose) \times 100%.

The frequency and reasons of apatinib dose reduction, treatment interruption, and permanent discontinuation will be summarized.

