6.4 Dose Modifications and Delay

6.4.1 General rules for dose modification

- Reasons for dose modification or dose delay, actions taken, and results should be recorded in the medical record and eCRF of the subject.
- For the accompanying symptoms that existed at baseline, the investigator shall determine whether to adjust the dose according to the grade of adverse drug reactions. For example, at baseline, a subject's Grade 1 "asthenia" at baseline that becomes Grade 2 "asthenia" during the study treatment period is one level increase of "asthenia". The dose should be adjusted as a Grade 1 toxicity

- If several adverse drug reactions of different grades or severity occur at the same time, the dose will be adjusted based on the highest level observed.
- If the dose is adjusted only due to abnormal hematological values, the dose will be adjusted based on the hematological values before the start of the treatment cycle.
- When the investigator judges that the adverse drug reaction is unlikely to further develop into a serious or life-threatening event, the current dose will be continued without dose modification or treatment interruption. In addition, no dose modification or treatment interruption is administered for anemia (non-hemolytic) because its symptoms can be relieved through blood transfusion.
- If, per the investigator's judgment, the toxic reaction is caused by a therapeutic drug, there is no need to adjust the dose of other drugs.
- Before PD, permanent discontinuation of a medication will not affect the continued administration of other treatments.
- If any treatment but not all drugs is interrupted due to adverse drug reactions of a drug, the treatment is still counted as a treatment cycle.

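### Apatinib compliance divides dosing days by treatment cycles, and no way of counting a partial cycle gives a fully adherent subject 100% in all three schedules at every stop day

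*SAP*

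**What the plan says.** SAP 5.3.2 defines apatinib compliance as actual dose over scheduled dose, in tablets at one per day.

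- **Numerator:** a count of days. "The actual number of days of administration is subject to the records of apatinib administration", and each dosing period contributes end date minus start date plus 1.
- **Denominator:** a count of cycles. It is "Scheduled dose (tablets): number of treatment cycles during the treatment period" times the entry in a table headed "Scheduled Number of Days of Administration in Each Treatment Cycle": 28 for daily dosing, 20 for 5 on/2 off, 14 for 7 on/7 off. The section adds that "One treatment cycle contains 28 days".

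Two things are left open: whether a partial cycle counts as one, zero or a fraction, and whether the treatment period ends with apatinib or with the last study drug.

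The neighbouring section, SAP 5.3.1, handles SHR-1210 differently and divides a scheduled duration by 14 days.

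Protocol 6.4.1 says that before progression "permanent discontinuation of a medication will not affect the continued administration of other treatments". It also says that when some but not all drugs are interrupted for adverse reactions, "the treatment is still counted as a treatment cycle". Protocol 6.4.2 contains interruptions and permanent stops that apply to apatinib alone. Protocol 7.2.3 ties end of treatment to confirmed progression or study withdrawal, not to the last apatinib dose.

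**The concern.** A compliance percentage should be 100% for a subject who took every scheduled tablet. Here the top of the fraction moves day by day while the bottom is tied to cycles, so the result depends on where in a cycle the subject stops and, for the on/off schedules, on whether the stop falls in an on-block or an off-block. SAP 5.3 reports drug use by dose group, and the groups differ only in apatinib schedule, so the artefact is not the same in each group.

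A second problem is that a subject taken off apatinib by the protocol's own rules, or held off it for a permitted interruption, can appear as non-compliant. Missed tablets and protocol-directed stopping are then merged in one figure.

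**Working it through.** **Inputs.** Cycle length 28 days and scheduled days 28/20/14 (SAP 5.3.2); the three schedules (Protocol 6.1.1); apatinib interruption allowed for up to 4 weeks (Protocol 6.4.2).

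**The plan's own figures.** Counting on-days over 28 days gives 28 for daily dosing, 4 × 5 = 20 for 5/2 and 2 × 7 = 14 for 7/7. All three agree with the SAP table. The per-cycle constants are right; the difficulty is the cycle count that multiplies them.

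**Formula.** Compliance = on-days taken ÷ (cycles × scheduled days per cycle), for a subject who takes every scheduled tablet.

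**Stop on day 7 of cycle 2 (day 35).** On-days taken: daily 35; 5/2 5 × 5 = 25; 7/7 7 + 7 + 7 = 21.

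| Cycle rule | Daily | 5/2 | 7/7 |
|---|---|---|---|
| Started (2) | 35/56 = 62.5% | 25/40 = 62.5% | 21/28 = 75% |
| Completed (1) | 35/28 = 125% | 25/20 = 125% | 21/14 = 150% |
| Fractional (35/28 = 1.25) | 35/35 = 100% | 25/25 = 100% | 21/17.5 = 120% |

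**Other stop days.**
- Cycles started, daily: day 14 of cycle 1 gives 14/28 = 50%; day 14 of cycle 2 gives 42/56 = 75%; day 14 of cycle 6 gives 154/168 = 91.7%.
- Cycles completed: undefined for any stop before the end of cycle 1, because the denominator is zero.
- Fractional cycles: daily dosing is exactly 100% at every stop day. For 5/2, a stop on day 5 gives 5 ÷ (5/28 × 20) = 140%. For 7/7, a stop on day 7 gives 7 ÷ (7/28 × 14) = 200%. By day 156 these are down to 100.5% and 101.3%.

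**Average over stop days 1 to 84.** Equal weight on each day is an illustrative assumption, not a figure from the documents.
- Cycles started: 70.5% (daily), 72.7% (5/2), 78.2% (7/7).
- Fractional cycles: 100%, 105% and 118%.

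**Are early stops plausible?** Protocol 2.3.1 cites median PFS of 1.4 to 2.8 months for checkpoint inhibitors in previously treated SCLC, about 43 to 85 days. Taking that as time on treatment (an assumption), an adherent daily-dosing subject scores 43/56 = 76.8% or 85/112 = 75.9% with cycles started.

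**Apatinib stopped alone, if every cycle of the overall treatment period counts.** Daily apatinib through cycle 2 with SHR-1210 to cycle 6: (2 × 28)/(6 × 28) = 56/168 = 33%. If only apatinib cycles count, the same subject is 56/56 = 100%.

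**One permitted 4-week interruption, daily dosing.** 28/56 = 50% over two cycles; 140/168 = 83.3% over six.

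**The case against.** The strongest reply is that this is an undefined term in a descriptive table, and that much of what a reader might infer goes too far. Four such inferences need limits.

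- **That adherent subjects are always reported far from 100%.** The text does not support this. The SAP does not prescribe whole-cycle counting; fractional counting makes daily dosing exact. Even with cycles started, a stop in the middle of cycle 6 gives about 92%. Day 7 of cycle 2 also ends a 7/7 on-block, an unfavourable point for the fractional rule; one week later the fractional result is 21/21 = 100%.
- **That Protocol 6.4.1 keeps adding cycles to the apatinib denominator after a permanent stop.** Its cycle-counting sentence concerns interruption. The sentence on permanent discontinuation says only that other treatment may go on. SAP 5.3.2 is the apatinib section, so counting only apatinib cycles is a natural reading, and the 33% is conditional.
- **That exposure or tolerability is misreported.** Actual dose comes from dosing records and is untouched. SAP 5.3.2 separately summarises apatinib reductions, interruptions and discontinuations with reasons, and SAP 5.5.1 analyses adverse events leading to them by drug.
- **That a decision is at risk.** The Stage II choice uses listings of adverse events and laboratory evaluations (SAP 6). Neither the per-protocol set (SAP 5.1.1) nor the important-deviation definitions (SAP 5.2.6) name a compliance threshold. Stage I has six subjects per group and one regimen goes forward, so a three-way compliance comparison carries little weight.

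All four limits stand. What the reply does not remove is that choosing a cycle rule would not cure the problem: none of the three gives 100% for full adherence across the schedules at every stop day. The formula needs replacing, not only a footnote.

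**Conclusion.** The point holds, as a minor one. The denominator is in different units from the numerator, and each available cycle rule misstates compliance for at least one schedule: downward in all three with cycles started, upward or undefined with cycles completed, upward in the on/off schedules with fractional cycles. The size depends on the unstated rule and on stop day; it is large for stops in the first two or three cycles and small in long courses. The 33% figure also requires the treatment period to mean the overall period, which the SAP does not state, although the end-of-treatment definition in Protocol 7.2.3 makes that reading possible. The consequence is confined to the compliance percentage by dose group. Nothing here bears on actual exposure, ORR, the analysis sets or the choice of regimen.

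**What to change.** In SAP 5.3.2, define the scheduled dose as the number of on-days of the assigned schedule from the first apatinib dose through one end date: the recorded date of the decision to discontinue apatinib permanently or, if apatinib was not stopped earlier, the end of treatment or the data cutoff.

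One date must be named. The last tablet and the discontinuation decision can be weeks apart when an interruption comes first, and ending the count at the last tablet would give 100% to a subject who simply stopped taking the drug.

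State also whether protocol-directed interruption days are removed from the denominator or reported separately. With that done, a subject who takes every scheduled tablet up to the end date scores 100% in all three schedules, whether or not SHR-1210 continues.

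The cost is a short SAP change and a small programming change. The downside is reliance on the recorded discontinuation date: on-days between the last tablet and a late-recorded decision would count as missed.

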5.4 Efficacy Analysis

5.4.1 Primary efficacy analysis

Based on the FAS, the number and percentage of subjects of BOR, ORR, and DCR are calculated by dose group, and 95% CIs are estimated using the Clopper-Pearson method.

The above analyses will be repeatedly conducted based on the PPS.

Handling of missing data: When calculating CR, missing data will be considered as cases not achieving CR, while the handling of PR, SD, and PD is the same as that of CR.

5.4.2 Secondary efficacy analysis

5.4.2.1 OS

The analysis of OS will be based mainly on the FAS.

The Kaplan-Meier product-limit approach will be used to calculate the median survival, its 95% CI will be calculated using the Brookmeyer-Crowley method based on log-log transformation, and the survival curves will be plotted. Also, the 6- and 12-month OS rates will be calculated using the Kaplan-Meier product-limit approach and their 95% CIs will be calculated using the pointwise method based on log-log transformation.

OS (months) is calculated as: $(OS \text{ event or censoring date} - \text{date of the first dose} + 1) / 30.4375$.

Missing data: This study will do everything possible to track subject survival until an OS event is observed. Inevitably, an OS event may not be observed for a subject before the end of the study, or a subject drops out before an OS event is observed, in this case, the time from the start date of randomization of this subject to the last observed survival date of the subject is taken as the subject's survival time, and this survival time is recorded as right censored data (the actual survival time is greater than the recorded time). If the date of death is incomplete, the day will be imputed with the earliest possible date.

5.4.2.2 PFS

The analysis of PFS will be based mainly on the FAS using the same method as that of OS.

PFS (months) is calculated as: $(PFS \text{ event or censoring date} - \text{date of the first dose} + 1) / 30.4375$.

The baseline tumor evaluation is defined as the last tumor evaluation before the first dose.

The date of visit corresponding to the PD as shown in tumor evaluation will be based on the earlier date of the following:

- The date of imaging examination showing a new lesion (if PD is based on the occurrence of a new lesion), or
- The date of the last imaging examination of observed lesions (if progressive disease is based on the increased total observed lesions). If there is no PD (including PR, CR, SD, and NE), the date of tumor evaluation will be based on the latest date recorded in the visit (target lesion or non-target lesion).

The censoring rules for PFS events are as follows:

For subjects experiencing PD or death:

- If a subject has begun a new anti-tumor treatment (excluding radiotherapy) before the PFS event, the date will be censored based on the date of the last tumor evaluation before the start of new anti-tumor treatment or the date of the first dose (whichever is later).
- Progressive disease or death after two or more scheduled tumor evaluations that are missing will be censored based on the date of the last tumor response evaluation before PD or death or the date of first dose (whichever is later). The missing of two or more scheduled tumor evaluations is defined as a situation where the interval between the event and the most recent tumor evaluation (including baseline) is longer than 126 days.

For subjects experiencing no PD or death:

- If there is no baseline tumor evaluation or post-baseline tumor evaluation (missing tumor evaluation or tumor evaluation as NE/NA at the corresponding visit), censoring will be based on the date of the first dose.
- If a subject has not experienced a PFS event on the end date of study/analysis or before dropout, the censoring will be carried out using the date of the last tumor response evaluation.

If the date of death is incomplete, the day will be imputed with the earliest possible date.

If the start date of the new anti-tumor treatment is incomplete, it will be imputed with the earliest possible date.

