5.4.2.4 DoR

DoR will only be analyzed for subjects with confirmed tumor response (CR or PR) after treatment. The censoring rules for DoR are the same as those for PFS, and the end date of response must be consistent with the date of progressive disease or death of the PFS. For DoR, the Kaplan-Meier product-limit approach will be used to calculate the median survival by treatment group, the corresponding 95% confidence interval (CI) will be calculated using the Brookmeyer-Crowley method based on log-log transformation, and the survival curves will be plotted.

DoR (months) is calculated as: (date of PFS event – date of the first documented CR or PR + 1) / 30.4375.

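### SAP 5.1.6.6 and 5.4.2.2 impute an incomplete start date of new anti-tumor therapy differently and state no precedence; read literally, 5.4.2.2 can replace an observed progression with an earlier PFS or DoR censoring

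*SAP*

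**What the plan says.** SAP 5.1.6.6 sets general rules for a missing start date of new anti-tumor treatment. Their stated purpose is narrow: "it will be imputed according to the following rules and used to derive the end date of the study treatment". The reference date is the smaller of two dates: (a) the later of PD + 1 and last dose + 1, and (b) the end date of the new treatment. On which PD is meant, it says: "The date of PD mentioned below is date of the first documented PD".

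- Known month and year match the reference date: "the date imputed = min [max (PD date + 1, date of the last dose + 1), end date of new anti-tumor treatment" (the formula's bracket closes there).
- Known month earlier: "the date will be imputed with the last day of MM". With only an earlier year known, 31 December is used.
- Known month or year later: the 1st of that month, or 1 January.

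The section ends by leaving other endpoints to their own text: "The rules for imputation of missing data for the remaining study endpoints will be detailed in the specific sections of analyses".

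SAP 5.4.2.2 then gives its own rule for PFS: "If the start date of the new anti-tumor treatment is incomplete, it will be imputed with the earliest possible date". The same section uses that date for censoring: "If a subject has begun a new anti-tumor treatment (excluding radiotherapy) before the PFS event, the date will be censored". The censoring date is the last tumor evaluation before the new treatment or the first-dose date, whichever is later. SAP 5.4.2.4 extends this: "The censoring rules for DoR are the same as those for PFS".

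**The concern.** The two sections can give different dates for the same field in the same subject, and the SAP does not say which one the PFS programmer should use. The closing sentence of 5.1.6.6 makes it reasonable to take the 5.4.2.2 rule, but it does not say that an endpoint section overrides 5.1.6.6.

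The choice matters because the start date decides whether a documented PD counts. A subject typically progresses and then moves to next-line treatment. If an incomplete start date is pushed back to the beginning of the month or year, the switch appears to come before the progression that caused it. The PD is then discarded and the subject is censored at an earlier scan. Such censoring is informative, because it falls on people known to have progressed, and it pushes Kaplan-Meier PFS and DoR upward. An early imputed date is not conservative here: an early death date shortens survival, whereas an early new-therapy date removes an event.

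**Working it through.** No figure in the plan depends on this rule, so there is none to reproduce. The check applies both rules, as written, to the same data.

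**Inputs.** Scans on day 28 and every 56 days after that (Protocol 8.1.2). PFS in months = (event or censoring date − first dose + 1) / 30.4375 (SAP 5.4.2.2). The earliest possible date is read as the 1st of the known month, or 1 January if only the year is known; that reading is an assumption, because the SAP does not define the term. Last dose is before PD, and no end date of the new therapy falls on or before PD.

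**Subject A.** First dose 5 Nov 2018; scans 2 Dec 2018, 27 Jan, 24 Mar and 19 May 2019; PD at the last of these.

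| Recorded start | Rule | Imputed start | PFS result |
|---|---|---|---|
| May 2019 | 5.1.6.6 | 20 May 2019 | event, 196/30.4375 = 6.44 months |
| May 2019 | 5.4.2.2 | 1 May 2019 | censored 24 Mar, 140/30.4375 = 4.60 months |
| 2019 | 5.1.6.6 | 20 May 2019 | event, 6.44 months |
| 2019 | 5.4.2.2 | 1 Jan 2019 | censored 2 Dec 2018, 28/30.4375 = 0.92 months |

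**Subject B.** First dose 4 Jun 2018; scans 1 Jul, 26 Aug and 21 Oct (PD); last dose 16 Oct; true start of new therapy 28 Oct. With the day missing, 5.1.6.6 gives 22 Oct and an event at 140/30.4375 = 4.60 months. SAP 5.4.2.2 gives 1 Oct, before both the PD and the last study dose, and censors at 26 Aug: 84/30.4375 = 2.76 months. With only the year known, it gives 1 Jan 2018, before first dose, and censors on day 1 (1/30.4375 = 0.03 months).

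**How often the event is lost when the day is missing.** It is lost when PD and the true start fall in the same month. With PD uniform over a 30.4-day month, the share is (30.4 − gap)/30.4. The enumeration below runs over every PD date in 2018-2019. It is slightly lower because a PD on the 1st is not preceded by the imputed date.

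| Gap from PD to new therapy (assumed) | Formula | Enumeration |
|---|---|---|
| 7 days | 23.4/30.4 = 77% | 74% |
| 14 days | 16.4/30.4 = 54% | 51% |
| 21 days | 9.4/30.4 = 31% | 28% |
| 28 days | 2.4/30.4 = 8% | 5% |
| 42 days | 0% | 0% |

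The share reaches zero at about 31 days. With only the year known, enumeration gives 98% at 7 days, 96% at 14, 92% at 28 and 88% at 42. Under 5.1.6.6 it is 0% at every gap tried (1 to 42 days), given the inputs above.

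**Effect on one group.** Simulated groups of 45 (the size in Protocol 10.1), with exponential PFS at a median of 13.3 weeks (the topotecan figure in Protocol 2.1.2). Assumptions not in the documents: half of progressors start new therapy 3-28 days after PD, and 10%, 20% or 30% of those start dates are incomplete.

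- Day missing: about 1.1, 2.1 and 2.8 PFS events lost per group under 5.4.2.2.
- Month and day missing: about 2.3, 4.3 and 6.5 lost.
- Under 5.1.6.6: none lost.
- The mean Kaplan-Meier median is higher under 5.4.2.2 by about 0.1-0.2 months (for example 4.17 against 3.99 with the day missing in 20%). With no missing dates, where the rules must agree, separate runs differed by 0.04 and 0.11 months, so the shift is close to simulation noise.

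**The case against.** **The earliest possible date is not defined as the 1st of the month or 1 January.** Protocol 6.5.2 prohibits other systemic anti-tumor therapy during the treatment period, so one could argue that a date before the last study dose is not possible, and that Subject A's year-only result is a worst case. It is a worst case. But the SAP states no lower bound: the limits at the end of 5.1.6.6 (consent withdrawal, loss to follow-up, death) bound imputed dates only on the late side. A programmer following the text has nothing to stop at.

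**Short gaps may be uncommon.** Protocol 8.1.2 requires a confirmatory scan 4 weeks (+ 7 days) after first imaging PD and dates a confirmed PD to its first discovery. Protocol 7.2.3 ties end of treatment to confirmed PD, and 6.1.2 allows treatment beyond first PD. A subject on that path has a gap of about 28-35 days or more, where few or no day-missing cases lose their event. This stands and limits the size. It does not remove the problem: Protocol 5.4.2 has subjects stop at PD unless they qualify to continue, so short gaps will occur, and year-only dates are affected at any of the gaps examined.

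**There may be one general rule and one endpoint-specific rule, by design.** That would explain why two rules exist. It would also mean that the rule which removes events is the one meant for PFS.

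**SAP 5.1.6.6 is not clean either.** It derives the start date from PD, which is itself the PFS event, and it is silent on subjects who die without documented PD. Both points stand and are taken up in the fix.

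**Conclusion.** The conflict is on the face of the SAP. Under a literal reading of 5.4.2.2, the conversion of an observed PD into an earlier censoring follows mechanically, and DoR inherits it. It is confined to incomplete start dates of non-radiotherapy treatment. The documents give neither the number of such dates nor the gap from PD to new therapy, so the shares and the simulated losses rest on the stated assumptions. The point merits correction before database lock; it does not threaten the trial's main conclusion.

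Four stronger readings might be inferred, and the documents do not support them:

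- *That 5.1.6.6 always places new therapy after PD.* If the known month or year is earlier than the reference date, or the new therapy ended on or before PD, the imputed date can still precede PD.
- *That half to three-quarters of day-missing cases lose their event.* That needs a gap of 7-14 days; at 28 days it is 5-8%.
- *That median PFS would be materially inflated.* The simulated shift is about 0.1-0.2 months, on secondary endpoints analyzed descriptively.
- *That the development decision is affected.* That rests on the response count (SAP 2.3 and 3). The earliest-date sentence sits in the PFS section and nothing extends it to BOR. However, SAP 4.1 ends BOR at the start of new therapy without saying which imputation applies, so BOR should be named in the correction.

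**What to change.** Replace the 5.4.2.2 sentence on the new-therapy start date with one along these lines: *Incomplete start dates of new anti-tumor treatment are imputed by Section 5.1.6.6 for PFS, DoR and BOR; where no PD is documented (for example, death without PD), last dose + 1 replaces max(PD + 1, last dose + 1) in the reference date.*

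In 5.1.6.6, widen the stated use beyond the end of study treatment. Also correct the lead-in, which restricts the rules to dates that are not completely missing although a completely missing date is one of the cases covered.

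The cost is about two sentences before database lock and no new data. There is a trade-off: a subject who truly switched shortly before PD in the same month would now count as an event, and PFS may look slightly less favourable because events are kept. A sensitivity analysis of PFS and DoR using the earliest possible date, with that term defined, would show how much depends on the choice. Reporting the number of incomplete start dates alongside it would let a reader judge its weight.
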